### 1.1.3 Trial interventions

- Counselling and procedures for obtaining parental consent for the study will commence when the neonate's platelet counts fall below 100  $\times 10^9/L$ .
- Neonates for whom parental consent has been obtained will be enrolled into the study when their platelet count has fallen below 50  $\times 10^9/L$  and randomised into one of two arms to receive prophylactic platelet transfusions triggered by either a platelet count below 25  $\times 10^9/L$  or below 50  $\times 10^9/L$ .

- Consented neonates with platelet counts below  $50 \times 10^9/L$  will be monitored using an updated version of a bleeding assessment tool, developed following the PlaNeT-1 study (Stanworth et al, 2009).
- Some neonates in each participating hospital may develop a new additional episode of thrombocytopenia (defined as platelet counts falling below  $50 \times 10^9/L$ ) after study day 14 during their hospital stay. These neonates will remain allocated to the same intervention arm for their entire length of stay in the participating hospital until discharge, death, 38 weeks Corrected Gestational Age (CGA), or Study Day 28 if this is later. In some cases Study Day 28 will fall after the baby has reached 38 weeks CGA if recruited after 34 weeks CGA.

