### **Data collection for assessment of outcome measures**

Evidence of all types of bleeding will initially be recorded in all neonates after randomisation up to Study Day 14 using a daily bleeding assessment tool, adapted for neonates from the WHO bleeding system of grading and the PlaNeT-1 study. In the PlaNeT-1 study, most major bleeds occurred within 14 days after birth, and neonates were more likely to show evidence of minor bleeding with thrombocytopenia in the first 10 days of life, than after 10 days.

- For neonates still in hospital at Study Day 14, daily bleeding assessments will cease and a weekly data collection form will be started and continued until the time of discharge, death, 38 weeks Corrected Gestational Age (CGA), or Study Day 28 if this is later. In some cases Study Day 28 will fall after the baby has reached 38 weeks CGA if recruited after 34 weeks CGA.
- Weekly data collection:  
The weekly data collection form will collect data on new major bleeds, mortality, platelet counts, platelet transfusions and cranial USS.
- Discharge home before Study Day 28:  
For those (occasional) neonates who are discharged home before Study Day 28, a telephone call follow-up by the local site research team to parents or GP will be made to determine if there were any serious adverse events in that time. Prior consent for telephone contact will be sought.
- End of Study:  
An End of Study form will be completed at the time of death, NICU discharge home, 38 weeks CGA or at Study Day 28 if this is later (for those neonates recruited after 34 weeks CGA). For neonates transferred whilst on the study to another unit participating in Planet, data collection will continue to end of study.
- Transfer out to non-participating units before Study Day 28:  

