### 4.2 Patient inclusion criteria for randomisation

1. Written informed consent obtained
2. Admission to a participating NICU (includes postnatal transfers)
3.  $<34$  weeks gestational age at birth
4. A platelet count of  $<50 \times 10^9/L$
5. Cranial ultrasound scan must have been undertaken less than 6 hours prior to randomisation in order to rule out recent major Intraventricular Hemorrhage (IVH) (refer to section 6.4 )

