### 5.2 Details of Registration Process and Randomisation

1. The local PI (or designate) will be responsible for identifying and consenting the parents/guardians of eligible neonates once the platelet count has dropped to  $<100 \times 10^9/L$ .
2. A screening sheet with a log number will be completed on all neonates admitted to selected participating units with platelets  $<100 \times 10^9/L$  and GA  $<34$  weeks. The log will include GA, post-natal age, birth weight and main diagnosis. It will include neonates not approached, and those neonates approached but in whom consent was not obtained for the trial (with reasons) and therefore will define how representative randomised neonates are as a group relative to the group of eligible neonates who were not randomised.
3. Eligibility for randomisation will be assessed with reference to inclusion and exclusion criteria.
4. When the neonate's platelet count falls to  $<50 \times 10^9/L$ , the PI or designate (the randomiser) will ensure a cranial ultrasound has been undertaken within the last 6 hours, and will then complete the trial registration/randomisation form and access the web based randomisation service at <http://www.sealedenvelope.com> to obtain a unique trial number and assignment of treatment policy. Before logging onto the website to randomise the neonate, the following pieces of information must be available: the neonate's gestational age at birth (in weeks and days); knowledge of presence or absence of IUGR; the most recent platelet count (which must be below  $50 \times 10^9/L$ ) and the date and time of the most recent cranial USS, which must have been undertaken within 6 hours before randomisation.
5. Following randomisation, the randomisation service will e-mail confirmation of the allocated treatment policy and trial number to the PI and Trial Manager. The PI will place the emailed allocated treatment policy in the neonate's medical notes.
6. The local PI/designate is responsible for informing the neonate's consultant and the parents of the neonate's treatment allocation, and for placing a label indicating trial participation on the cot and cover of the neonate's medical notes.

7. The local PI/designate will complete the patient's screening sheet adding the patient's trial number to the existing data. The local PI/designate will also be responsible for informing the Blood Bank of the trial number and the trial treatment allocation.

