### 7.4 Randomisation

Background data will be collected before or at the time of randomisation including:

- gestational age at birth
- weight at birth
- gender
- postnatal age in days
- weight at enrolment
- co-existing or prior medical conditions/ diagnosis including major bleeds, IUGR, NEC  $\geq$  Stage 2 defined as per Bell's criteria (Bell et al; 1978) and sepsis

Once final eligibility is confirmed, the neonate will be randomised into the study according to the procedures described in Section 5

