## 9 OUTCOMES & STATISTICAL CONSIDERATIONS

### 9.1 Randomisation

A web-based randomisation service provided by (<http://www.sealedenvelope.com>) accessible by each participating centre will allocate neonates using minimisation with a random element.

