### **9.2.2 Secondary outcomes**

Secondary outcomes include:

- Proportion of patients surviving to go home following a major bleed, censoring at discharge
- Proportion of patients surviving to go home without having had a major bleed, censoring at discharge
- Proportion of patients who have died up to study day 28
- Proportion of patients who sustain a major bleed up to study day 28
- The rate and time from randomisation of minor, moderate and major bleeding derived from the bleeding assessment tool up to study day 14, and for major bleeds up to study day 28. Definitions for all grades of bleeds are shown in the bleeding assessment tool; grading will be assigned based on a modified version of the WHO Bleeding Score
- Number of platelet units transfused up to study day 28
- Time to discharge home, censoring on death
- Neuro-developmental outcome as assessed by the Thames Regional Perinatal Outcome Group/ Standard Electronic Neonatal Database/ National Neonatal Audit Programme (TRPG/SEND/NNAP) 2- year corrected age outcome form at 2 years corrected postnatal age. This will provide a basis of correlation with the WHO functional disability score.
- Platelet transfusion-related adverse events from the time of randomisation up to end of study (section 7.6 and 8.3.2)

A comprehensive statistical analysis plan will be written before the final data analysis is conducted. Analysis of all outcomes will be conducted on the basis of intention to treat. The primary analysis will be adjusted for the stratifying variables.

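### Postnatal age at entry, already recorded and plausibly prognostic, could be added to the stated adjustment of the primary analysis at almost no cost

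*Protocol*

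**What the plan says.** - **Adjustment.** Section 9.2.2 says "The primary analysis will be adjusted for the stratifying variables", immediately after announcing a statistical analysis plan and an intention-to-treat basis.
- **Allocation.** Section 9.1 says the web service "will allocate neonates using minimisation with a random element". It lists no factors.
- **Information needed to randomise.** Section 5.2, item 4 requires "the neonate's gestational age at birth (in weeks and days); knowledge of presence or absence of IUGR", the latest platelet count, and the date and time of the latest cranial scan. Postnatal age does not appear.
- **Eligibility.** Section 4.2 restricts "weeks gestational age at birth" to below 34. Neither 4.2 nor 4.3 restricts age at randomisation. Section 1.1.3 foresees late entry: "In some cases Study Day 28 will fall after the baby has reached 38 weeks CGA if recruited after 34 weeks CGA".
- **Relevance of age.** Section 2.1 names post-natal age, beside gestational age, among the sources of clinical diversity that complicate transfusion thresholds. Section 1.2, under data collection for assessment of outcome measures, reports that in PlaNeT-1 "most major bleeds occurred within 14 days after birth, and neonates were more likely to show evidence of minor bleeding". The comparison for minor bleeds sets thrombocytopenic infants up to day 10 of life against older ones.
- **Availability.** Section 7.4 collects "postnatal age in days" before or at randomisation.

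**The concern.** The 28-day outcome clock starts at randomisation. An infant entered on day 2 of life is followed through most of the period in which the PlaNeT-1 major bleeds clustered. An infant born at 24 weeks and entered after 34 weeks corrected age is at least 34 - 24 = 10 weeks old and is followed through none of it. Two such infants can share gestation at birth and IUGR status, so balancing or adjusting on those two does not separate them.

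If age at entry predicts the primary outcome and is neither balanced nor adjusted for, two things are lost: some precision that the collected data could supply, and some protection against a chance excess of early entrants in one arm.

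**Working it through.** **1. The plan's own figure.** Section 9.3 gives 20% versus 12%, two-sided 5%, 80% power. With pooled variance and no continuity correction:

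n = [1.960·√(2·0.16·0.84) + 0.842·√(0.20·0.80 + 0.12·0.88)]² / 0.08² = 328.5, so 329 per group.

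This matches the protocol. At 330 per arm (660 in total) power is 80.2% by this formula and 80.5% with unpooled variance. The unpooled figure is the baseline below.

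**2. Assumptions.** The protocol gives no event rate by postnatal age. Age is treated as early or late, with early share f = 50%, 70% or 85% and early-versus-late odds ratio 1.5, 2, 3 or 5. Overall risks are held at 20% and 12%. The comparison is between no adjustment and adjustment for age alone.

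**3. Formulas, n = 330 per arm.** Let e and l be the early and late risks in each arm.

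- Unadjusted variance: (0.20·0.80 + 0.12·0.88)/330 = 8.05×10⁻⁴.
- Adjusted variance: the f-weighted within-stratum binomial variances of the two arms, divided by 330, plus the variance of the stratum-specific risk differences divided by 660.
- Power: Φ(0.08/√variance - 1.96).
- 95% chance imbalance in early share: 1.96·√(2f(1-f)/330).
- Shift in the risk difference: that imbalance times the early-late risk gap averaged over the arms.

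**4. Most favourable case (f = 0.5, odds ratio 5).** The risks that satisfy the constraints are 0.316 and 0.084 in Arm A, and 0.194 and 0.046 in Arm B.

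- Within-stratum part: 7.48×10⁻⁴. Second part: 0.03×10⁻⁴. Total: 7.50×10⁻⁴, a reduction of 6.8%.
- Power: Φ(0.960) = 83.2%. Equivalent n: 329 × 0.932, so 307 per arm.
- Imbalance: 1.96·√(0.5/330) = 7.6 points. Average gap: 19.0 points. Shift: 0.076 × 0.190 = 1.4 to 1.5 points.

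**5. Across the range.**

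| Early share | Odds ratio | Variance reduction | Power, from 80.5% | Equivalent n per arm | Shift at 95% imbalance |
|---|---|---|---|---|---|
| 50% | 1.5 | 0.5% | 80.7% | 328 | 0.41 points |
| 50% | 5 | 6.8% | 83.2% | 307 | 1.45 points |
| 70% | 2 | 1.1% | 80.9% | 326 | 0.58 points |
| 70% | 5 | 3.9% | 82.0% | 317 | 1.10 points |
| 85% | 1.5 | 0.2% | 80.6% | 329 | 0.27 points |
| 85% | 5 | 1.8% | 81.2% | 323 | 0.75 points |

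**6. Simulation.** Logistic regression, 3,000 runs per case, 70% early, odds ratios 2, 3 and 5. Power was 80.3%, 80.4% and 80.4% without the covariate, and 80.9%, 81.4% and 81.9% with it. Type I error was 4.5-5.3% either way.

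**The case against.** The other side has four good arguments.

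- **Covariates belong in the analysis plan.** The announced plan is not available here, and a covariate list is often completed there. This stands in part. But 9.2.2 does not leave adjustment open: it states a set, so a recommendation about that set is fair. The text does not say that only these variables will be used. A reader might infer that postnatal age is ruled out, and the sentence does not support that.
- **The stratifying variables are unnamed.** A reader might take it as fact that postnatal age is not among them. Section 5.2 only suggests so: it lists what must be to hand at log-on, and some of those items serve eligibility checks. If postnatal age is a minimisation factor after all, the stated adjustment already covers it.
- **The prognostic evidence is thin.** A reader might infer that the protocol shows age to be a strong predictor. It does not. The 14-day statement has no denominator by age and may partly reflect when infants were thrombocytopenic. The 10-day statement concerns minor bleeds, which are outside the primary outcome. Nothing is given on deaths by age. Other baseline variables, such as weight, sepsis and NEC, are also collected and could be argued for. Postnatal age stands out only because the protocol itself remarks on it and late entry makes it vary widely.
- **No bias follows.** A reader might infer that leaving the covariate out distorts the result. In a randomised comparison it neither biases the test nor inflates type I error, as the simulation shows, and chance imbalance is already reflected in the confidence interval.

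All four limit the size of the point. None makes the added covariate costly or unhelpful.

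**Conclusion.** This is a free improvement of low severity. No stated figure is wrong, and adjusting for allocation factors is a defensible choice. What remains is a modest loss of efficiency: about 0.1 to 2.7 points of power, at most 22 infants per arm in equivalent sample size (329 - 307), and a possible shift of 0.3 to 1.5 points in the unadjusted risk difference.

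These sizes rest entirely on the assumed early share and odds ratio. They also treat early entry as if balanced only by chance and compare with no adjustment at all. To the extent that gestation and IUGR already carry the same information, the real gain would be smaller.

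**What to change.** In section 9.2.2, state that the primary analysis will be adjusted for the minimisation factors and also for postnatal age at randomisation, with its functional form (continuous, or a split stated in advance) fixed before unblinding. Carry the same wording into the analysis plan. Naming the minimisation factors in section 9.1 would also settle whether postnatal age is already among them.

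The cost is one sentence in each document. Section 7.4 already collects the variable, and allocation and recruitment stay as they are.

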### 9.3 Sample size

This trial (PlaNeT-2) represents the first trial in the field of neonatal platelet transfusion prophylaxis in this population of preterm neonates. This study has been designed as a two stage trial with an interim analysis which will inform the final sample size requirement and trial feasibility (See Section 9.4). Data on the frequency of bleeding outcomes in severely thrombocytopenic neonates is available from the PlaNeT-1 survey (Stanworth et al, 2009), in which 30/169 or 18% of neonates died or experienced a major bleed while on study. However, this proportion applies to neonates of all gestational ages, and only during episodes of significant thrombocytopenia. Overall mortality (and new major bleeds) is likely to be greater than this figure derived from PlaNeT-1 data for the baseline event rate in the arm A of this trial. Assuming a proportion of 20% for the primary outcome for Arm A, in order to detect a difference between proportions of 8% (assuming that the proportion in Arm B is 12%), using a two-sided test, 5% significance level and 80% power, 329 neonates in each group is needed. Rounding this figure up, a total of 660 neonates will be required for this study. Note that this calculation does not take account of withdrawals or loss to follow-up.

The Data Monitoring Committee (DMC) will be closely monitoring the primary outcome (mortality and major bleeds) as well as safety data for any imbalance between the two arms (See Sections 10, 11 for further details).

### 9.4 Interim analysis

The trial has been designed as a two-stage, superiority randomised trial with an interim analysis performed after 100 neonates have been recruited. The main purpose of the interim analysis is to provide a good estimate of the event rate for the primary outcome in the standard arm A, and to review the final sample size requirement and need for additional recruiting centres. No conclusions based on possible emerging benefits between the two arms will be drawn. Using data from the PlaNeT-1 study, we currently estimate that it will take 18-24 months to recruit 100 patients. Data from the interim analysis will help refine these estimates and help plan the number of centres and length of time needed to reach the required sample size. Additionally, the numbers of platelet transfusions and protocol violations affecting per protocol analysis will help determine the feasibility of this study.

The trial statistician will prepare regular reports of trial progress and serious adverse events for the DMC.

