# 1 SUMMARY

## 1.1 Abstract and summary of trial design

A trial assessing clinically relevant outcomes in relation to the platelet count thresholds commonly used as triggers for transfusion has never been undertaken in preterm neonates with severe thrombocytopenia. Practice in many neonatal units in UK has seen the adoption of thresholds for prophylactic platelet transfusions at around 20 to 30  $\times 10^9/L$ , but the effectiveness and safety of any thresholds in preterm neonates has not been established in randomised controlled trials. In the only randomised controlled trial to assess a threshold level for the effectiveness of neonatal prophylactic platelet transfusions, the platelet count thresholds were 50 and 150  $\times 10^9/L$  (Andrew et al, 1993), but this trial excluded neonates with platelet counts  $< 50 \times 10^9/L$ .

Platelets for Neonatal Transfusion - study 2, (PlaNeT-2) is a 2-stage, randomised, parallel group, superiority trial, which follows on from a prospective multicentre observational study of platelet transfusion practice in neonates (PlaNeT-1 study; Stanworth et al, 2009). PlaNeT-2 compares clinical outcomes in preterm neonates randomised to receive prophylactic platelet transfusions to maintain platelet counts at or above either 25  $\times 10^9/L$  or 50  $\times 10^9/L$ . An interim analysis to assess trial feasibility and re-calculate the sample size will be conducted after 100 patients have completed the study period for the primary outcome.

PlaNeT-2 aims to assess whether a higher prophylactic platelet transfusion threshold is superior to the lower thresholds in current standard practice in reducing the proportion of patients who experience a major bleed or death up to study day 28. This trial will help define optimal platelet transfusion support for severely thrombocytopenic preterm neonates by evaluating the risks and benefits of two different prophylactic neonatal platelet transfusion thresholds highlighted by the PlaNeT-1 study. If superiority is demonstrated then it would have an important influence on clinical practice. If superiority is not demonstrated for a higher platelet count threshold, the potential benefits of the lower threshold in neonatal practice include fewer transfusions, reduced donor exposure, less risk of platelet transfusion related adverse effects, including errors in processing and administration, and reduced costs (see section 2).

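### The interim sample-size review rests on an Arm A event rate from about 50 infants, too few for the precision claimed, and its trigger is stated two ways

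*Protocol*

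**What the plan says.** Section 9.3 sizes the trial "using a two-sided test, 5% significance level and 80% power". It reads "Assuming a proportion of 20% for the primary outcome for Arm A", takes 12% for Arm B, and concludes that "329 neonates in each group is needed", rounded up to 660 in total. Loss to follow-up is not included.

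Section 9.4 describes two stages "with an interim analysis performed after 100 neonates have been recruited". The analysis is chiefly meant to "provide a good estimate of the event rate for the primary outcome in the standard arm A". That figure then feeds a review of the total number of infants and of whether more centres are needed. It rules out conclusions about benefit between the arms. Sections 10.1.1 and 14 also count 100 infants recruited.

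Section 1.1 gives a different trigger. There the interim analysis, which assesses feasibility and re-calculates the sample size, "will be conducted after 100 patients have completed the study period for the primary outcome".

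**The concern.** Refining the sample size is a stated purpose of the first stage, and section 9.4 attributes to the Arm A estimate a precision that about 50 infants cannot give. If the size is revised on that figure, chance alone could halve the trial or enlarge it by half.

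Two further matters follow from the same paragraph. Estimating the rate in one arm requires outcome data split by allocation, and an Arm A rate read beside the overall count gives the Arm B rate. The two triggers also define different data sets: under the recruited wording, the latest infants have no Study Day 28 outcome when the analysis falls due.

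**Working it through.** **Inputs.** From section 9.3: 20% in Arm A, 12% in Arm B, difference d = 0.08, two-sided 5%, 80% power. From section 9.4: 100 infants, recruited over 18 to 24 months. Assumed: 1:1 allocation (implied by the equal groups), so about 50 in Arm A; 10/50 events in Arm A and 16/100 overall, which are the planned rates; all infants evaluable.

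**1. The protocol's figure.** With q = 1 − p and p̄ the mean of the two rates,

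n per arm = [1.960 √(2 p̄ q̄) + 0.842 √(pA qA + pB qB)]² / d².

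- 2 p̄ q̄ = 2 × 0.16 × 0.84 = 0.2688.
- pA qA + pB qB = 0.1600 + 0.1056 = 0.2656.
- n = (1.0162 + 0.4337)² / 0.0064 = 328.5, so 329 per arm and 658 in total. This reproduces.

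**2. Precision of the Arm A rate.**

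- SE = √(0.20 × 0.80 / 50) = 0.0566, or 5.7 points.
- Wilson 95% interval for 10/50: 11.2% to 33.0%. The exact interval is 10.0% to 33.7%.
- For comparison, the 30/169 that section 9.3 cites from the earlier observational study has SE √(0.1775 × 0.8225 / 169) = 2.9 points. Section 9.3 notes limits to its relevance, but the interim estimate has about twice its standard error.

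**3. Effect on the recalculated size, 8 points held.**

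| Arm A rate | Arm B rate | Total |
|---|---|---|
| 11.2% | 3.2% | 328 |
| 20% | 12% | 658 |
| 33.0% | 25.0% | 1,010 |

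1,010 / 328 = 3.1, a three-fold range.

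**4. The pooled rate instead.** When d is fixed, pA qA + pB qB = 2 p̄ q̄ − d²/2 (check: 0.2688 − 0.0032 = 0.2656). The formula then depends on the data only through p̄, so no split by arm is needed.

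- SE = √(0.16 × 0.84 / 100) = 0.0367, or 3.7 points.
- Wilson 95% interval for 16/100: 10.1% to 24.4%.
- Totals at these limits: 444 and 904. 904 / 444 = 2.0, a two-fold range.
- With d held, p̄ is the Arm A rate minus 4 points, so the Arm A route carries the full 5.7-point SE into p̄. Pooling cuts it by 1 − 3.67/5.66 = 35%.

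**5. What pooling costs if the effect is not 8 points.** If both arms are truly 20%, then p̄ = 20%. With d held, the formula is evaluated at 24% v 16% and gives 784, against 658 from an Arm A rate of 20%: 126 infants more.

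**6. The trigger.** Accrual is 100/24 = 4.2 to 100/18 = 5.6 infants a month, and 28 days is about 0.92 months. So 3.8 to 5.1 infants, about 4 to 5, would not have reached Study Day 28 when the hundredth is recruited.

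**The case against.** Observing the control rate directly is a legitimate choice, because it does not rest on the effect under test. This stands in part: step 5 shows that the pooled route shifts the size when the true difference is not 8 points. A larger bias arises if the Arm A rate is inferred through an assumed risk ratio of 0.60 (a pooled 20% would imply 25%), but holding the absolute difference avoids that step.

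Pooling also leaves a two-fold range, so it improves the estimate only moderately. That stands.

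Section 9.4 speaks of reviewing the size, lists other purposes (centres, recruitment time, transfusions, protocol violations) and sets no mechanical rule. That stands too, though section 1.1 does speak of re-calculation and the wording about precision remains wrong.

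Three stronger readings are tempting and are not supported:

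- **That the recalculated size is almost unconstrained.** The range is wide but bounded, at 328 to 1,010.
- **That the interim analysis discloses an arm-level result.** No section releases the Arm A rate to investigators. Section 9.3 already has the Data Monitoring Committee watch the primary outcome for imbalance between the arms, and section 11.3 has it review outcomes for feasibility. A committee charter, not shown, could limit access. Ruling out conclusions about benefit does not rule out estimating one arm's rate, so there is no contradiction either.
- **That the effect to be held is open, so one result could move the size either way.** Holding a 40% relative reduction would give 1,270 down to 348 over the same interval. But section 9.3 names only the absolute target: "in order to detect a difference between proportions of 8" per cent.

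**Conclusion.** The point holds on two counts. An Arm A rate from about 50 infants, with a standard error of 5.7 points and a 95% interval of 11% to 33%, does not have the precision that section 9.4 claims; it allows a three-fold range of totals around 660. And the trigger contradicts itself between section 1.1 and sections 9.4, 10.1.1 and 14. The second matters less: about 4 to 5 infants, or roughly a month's wait.

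Using data by arm is an avoidable risk, not a demonstrated breach. The sizes rest on 1:1 allocation, the planned event rates, complete outcomes and the 8-point difference being held. The calculation of 329 per group is correct and is not in question.

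**What to change.** - In section 9.4, base the review on the pooled event rate, blind to arm, in the first 100 infants who have completed Study Day 28, and state that the 8-point difference of section 9.3 is held.
- Use that single trigger in sections 1.1, 9.4, 10.1.1 and 14.
- Replace the description of the estimate as good with its expected precision: a standard error of about 3.7 points at a pooled rate of 16%, with totals from about 444 to 904.
- Section 14 says that funding has been extended to the whole trial, which may mean that the interim analysis has already taken place. If so, record which rate and which trigger were used.

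The change is one of wording, plus about a month's wait if the recruited trigger would otherwise have been followed. The costs are that the Arm A rate is no longer observed directly, that the size shifts if the true difference is not 8 points (about 784 instead of 658 if both arms are at 20%), and that the range narrows only moderately.
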